 All laboratory tests to be done locally, unless otherwise noted. When laboratory tests are obtained on the same day as NEOD001 administration they should be obtained *prior to* administration of study drug. Pregnancy tests for WOCBP as follows: **Screening:** serum test within 28 days before Month 1-Day 1; **Month 1:** serum test within 24 hours before Month 1-Day 1; **Months 2-12:** serum test preinfusion; **EOS/ETD:** serum test; **90 ( $\pm 5$ ) days after the last study drug administration:** serum test.

 Serum free light chain studies, U-PEP, U-IFE, SPEP and S-IFE will be obtained prior to administration of NEOD001 or placebo.

[figure not shown]
 Archive of baseline and confirmatory EOS visit urine samples, in consenting patients, from first morning urination will be maintained at Tufts. Samples should be obtained during the screening period before the renal biopsy. Samples will be shipped same-day overnight in kits provided. These samples will be banked for future unspecified testing.

 Renal biopsy at study entry is standard of care. Renal biopsy should be obtained after mGFR and other urine studies, including archived urine sample, have been performed. A portion of the biopsy is routinely used for frozen section and, in consenting patients, will be cryopreserved in RNA Later for future molecular testing.

 Standard-of-care follow up will include local testing every 3 months of all laboratory studies included in the confirmatory visit during the OLE study.

 Inflammatory biomarkers include IL-6, IL-8, TNF $\alpha$ , C3 and C4, CRP, SAA (A-SAA), and tryptase (at screening only). Biomarkers should be repeated if clinically indicated, i.e. the subject has a hypersensitivity reaction.

 Serum creatinine and 24 hour urine collection, including UPEP, to be sent to central lab (Covance).

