## 3 STUDY PLAN

### 3.1 Study Design

This is a multicenter Phase 2b, randomized, double-blind, placebo-controlled, two-arm, parallel-group efficacy study of NEOD001 as a single agent administered intravenously in adults with AL amyloidosis who had a hematologic response (Appendix 1) to previous treatment for their AL amyloidosis and have persistent renal dysfunction due to AL amyloidosis.

Subject screening will occur during the 28 days prior to the first administration of study drug (i.e., month 1 day 1). If all other eligibility requirements are met, the subject will undergo renal biopsy and, if AL amyloid is confirmed as the cause of renal disease, all screening assessments will be completed and the patient will be enrolled in RAIN. Screening assessments are listed in Table 1. Patients will have a renal biopsy to confirm that the basis of renal dysfunction is amyloidosis and may have renal function studies measuring urinary clearance of iothalamate (Conray® - iothalamate meglumine injection U.S.P 60%; Mallinckrodt Inc., St. Louis, MO) from the blood. The renal function studies require 1 day and will be performed prior to the renal biopsy. Month 1 day 1 start of therapy will occur at least 2 days after the renal biopsy.

Study visits will occur every 28 days based on scheduling from month 1 day 1. A  $\pm$ 5-day window is allowed for visits starting after month 1. Subjects may receive up to 12 infusions of study drug. Subjects who discontinue study drug before the initial EOS visit should have an Early Treatment Discontinuation (ETD) visit 30 ( $\pm$ 5) days after their final administration of study drug. After completing 12 months of treatment and the initial EOS visit, each patient will return one month later for a confirmatory EOS visit in order to confirm the results of renal testing obtained at the initial EOS visit.

After completing 12 months of treatment with NEOD001 or placebo and the confirmatory EOS visit, a subject may enter an open-label extension (OLE) study, during which subjects will receive active treatment with NEOD001 for 12 months and may receive concurrent chemotherapy.

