#### **3.2.3 Ancillary Studies**

Ancillary studies for this trial are being performed in collaboration with the Amyloidosis Research Consortium (ARC; described in synopsis). ARC will maintain ancillary study data in a REDCap database that the Tufts Neely Center for Clinical Cancer Research will create and oversee. The ancillary studies are being performed by a collaborative of Tufts, the ARC and for the gene expression work the University of Michigan. This work is being conducted under CDA and with IP agreements and carve-outs currently being negotiated. Patients will be assigned alphanumeric characters (absent all personal identifying information) that are linked to the Case

Report Forms maintained in REDCap by the participating centers and the Tufts Neely Center for Clinical Cancer Research.

The ancillary studies are designed in order to determine if there are differences among patients who receive NEOD001 and those who do not, and to define and identify differences among patients who have renal responses and those who do not, and renal progression or not, whether or not those patients receive NEOD001.

- Patient reported outcomes: Patients who receive NEOD001 or have renal responses or renal progression may experience changes in their quality of life. Patient reporting of outcomes is very important to in order to answer whether changes in renal disease status are associated with changes in quality of life. We will obtain SF-36 surveys at study entry and at 3, 6, 9 and 12 month visits and at ETD or initial and confirmatory EOS visit (Appendix 7). Scores will be computed and comparisons made by norm-based scoring (User's Manual for the SF-36v2 Health Survey, Second Edition).

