- Renal Pathology Studies: We hypothesize that the findings related to amyloid and to renal injury in entry renal biopsies will correlate with risk of progression of renal disease and possibly with likelihood of responding to NEOD001. Renal biopsies containing amyloid as the critical factor in renal dysfunction will also contain some pattern of intrinsic renal injury with findings related to glomerulosclerosis, tubular atrophy and interstitial fibrosis. We will score the screening renal biopsies for amyloid load and pattern of infiltration as well as for these intrinsic renal injury patterns. (Appendix 8). Results of renal biopsy scoring will be recorded by ARC. The renal pathology group will use established criteria and perform the scoring using a standard operating procedure and data sheet. Comparisons will be made between the various groups, and among confirmed renal responses in the NEOD001 and placebo groups, by the CMH test stratified by the pre-randomization stratification factors at alpha of 0.05.

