### 8.3.3 Ancillary Studies Analyses

The ancillary studies analyses will be performed by the Amyloidosis Research Consortium (ARC) in collaboration with Tufts Medical Center and the other RAIN study centers. Original forms will be faxed or reported electronically to the ARC data manager for entry into the RAIN ancillary studies database. The ancillary studies database will be maintained by ARC personnel and be accessed by Tufts and ARC data managers. This database is part of the secure REDCap database that is used for this trial.

SF-36 surveys (Appendix 7) will be scored and recorded in a central REDCap data bank. The SF-36 assesses 8 scales of health status from which a physical component summary (PCS) and a mental component summary (MCS) are derived (User's Manual for the SF-36v2 Health Survey, Second Edition). Summary scores will be standardized so a score of 50 corresponds to the average for the US population. Baseline and follow-up SF-36 scores will be compared for each patient and with population norms using 1-sample t tests. Pearson correlations, t tests, Wilcoxon 2-sample tests, and Mantel-Haenszel tests will be used to describe the associations between various component scales and scores of the SF-36 and clinical and demographic characteristics of these patients. The relationship of improvement or worsening in the PCS or MCS to 12 months of treatment with NEOD001 or placebo, and also to the presence or absence of confirmed renal responses, will be examined using the Mantel-Haenszel test. In order to determine whether the QOL measures reflect contributions that were independent of or equivalent to those made by treatment assignment, presence or absence of confirmed renal responses, or clinical characteristics, stepwise proportional hazards regression with the significance level for entry into and for staying in the model set at 5% will be used to identify clinical and health status factors related to changes in QOL measures from the beginning to the end of treatment.

Renal biopsies will be scored by a predefined set of criteria for the degree and pattern of amyloid involvement and distribution (Appendix 8). The renal pathology group will use established criteria, perform the scoring using a standard operating procedure and record results in a central data bank. Comparisons will be made between the NEOD001 and placebo groups by the CMH test stratified by the pre-randomization stratification factors at alpha of 0.05.

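### For renal biopsy scoring, Section 8.3.3 and the synopsis specify only an arm comparison on a pre-randomisation biopsy and omit the outcome contrasts planned in Section 3.2.3

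*Combined protocol and SAP*

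**What the plan says.** Section 8.3.3, on biopsy scoring: "Comparisons will be made between the NEOD001 and placebo groups by the CMH test stratified by the pre-randomization stratification factors at alpha of 0.05". The synopsis repeats the sentence under Renal Biopsy Scoring. Neither place relates a biopsy score to an outcome.

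Section 3.2.3 has a different aim. Its hypothesis is that "findings related to amyloid and to renal injury in entry renal biopsies will correlate with risk of progression of renal disease", and possibly with the chance of responding to NEOD001. The ancillary studies as a whole are meant "to define and identify differences among patients who have renal responses and those who do not, and renal progression or not", whichever arm the patients are in. For biopsies it plans: "Comparisons will be made between the various groups, and among confirmed renal responses in the NEOD001 and placebo groups", by CMH with the same strata and alpha. Biopsies are to be scored for amyloid load and pattern "as well as for these intrinsic renal injury patterns".

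On timing, Table 1 marks a renal biopsy at screening only, and its footnote says "Renal biopsy at study entry is standard of care". Section 3.1 adds: "Month 1 day 1 start of therapy will occur at least 2 days after the renal biopsy". Section 6.1.2.1 places randomisation on month 1 day 1, before the infusion.

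Appendix 8 defines two composites: an amyloid score (AS), the sum of four compartment scores, and a Composite Scarring Injury Score (CSIS), the sum of percent global sclerosis and percent tubulointerstitial fibrosis.

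**The concern.** The scored tissue predates treatment allocation, so the arm test in 8.3.3 carries no information about what the drug does. It is also silent on prognosis, because no outcome enters it. A significant result among all randomised patients would be a chance imbalance; a non-significant one would say nothing about the hypothesis. The contrasts that bear on the hypothesis appear only in 3.2.3, in loose terms. Response is named there, but progression has to be read from the hypothesis, the general aim and the reference to various groups. An analyst working from the statistical section would run the uninformative test and could leave out the informative ones.

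**Working it through.** **1. The plan's own figure.** The only power statement is for the primary endpoint (Section 8.5): 25% versus 55%, alpha 0.05, power 0.8. Taking alpha as two-sided, as in Section 8.3.1:

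n = [1.960·√(2·0.40·0.60) + 0.842·√(0.25·0.75 + 0.55·0.45)]² / 0.30² = (1.358 + 0.555)² / 0.09 ≈ 40.7, so 41 per arm.

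Power at 41 per arm is 0.803, and 41/0.82 = 50 per arm after 18% dropout. The plan's figures reproduce. They set the trial size used below; the point does not depend on them.

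**2. Order of events.** Section 1.1 requires the screening biopsy before a patient is declared eligible, and stratification and randomisation follow. The biopsy is at least 2 days before month 1 day 1. No later biopsy is scheduled. The score is therefore fixed before allocation.

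**3. What the arm test can detect.** Let S be the score and A the arm. Randomisation within strata makes S independent of A given stratum, which is exactly the CMH null. The rejection rate among all randomised patients is then about alpha, whatever the relation of S to outcome.

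A simulation illustrates this (10,000 runs, 50 per arm, four equal strata, a binary score split 50/50; the split, the strata and the links are assumptions). Every scenario keeps average response at the plan's 25% and 55%. Response rates are for the favourable versus the unfavourable score.

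| Assumed link | Arm vs score (8.3.3) | Response vs score | Response vs score, NEOD001 only |
|---|---|---|---|
| None | 5.6% | 4.5% | 5.2% |
| Prognostic: placebo 40% vs 10%, NEOD001 70% vs 40% | 5.5% | 86.8% | 54.1% |
| Effect modification: placebo 25% vs 25%, NEOD001 85% vs 25% | 5.4% | 87.5% | 99.4% |

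The 8.3.3 test stays near 5% throughout, while a test of response against score picks up both links. That pooled test rejects about equally often under prognosis and under effect modification, so it cannot tell them apart. A score-by-arm interaction is needed for that.

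**4. The comparison among confirmed responders (3.2.3).** This selects on an outcome after randomisation. In the prognostic row the drug adds 30 points at either score level, yet the share of responders with the favourable score is 40/(40+10) = 80% on placebo and 70/(70+40) = 64% on NEOD001. With equal odds ratios in both arms (a separate simulation of AS, 41 per arm), the responders-only comparison rejects in 5.2%, 5.8%, 7.5% and 9.0% of runs at odds ratios of 1, 1.5, 2 and 2.5 per SD, although there is no interaction. A logistic interaction test with equal odds ratios of 2 in both arms rejects in 5.2%. The responders-only contrast therefore does not isolate prediction of response to NEOD001.

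**5. Power of the replacement, as illustration only.** The documents give no score distribution, score effect or progression rate. Assumed: component correlation 0.4, equal-probability categories, 30% PR, 30% renal stage 3, score independent of strata, odds ratio 2 per SD, 41 per arm. Power for AS against progression is then 20%, 37%, 50% and 69% at progression rates of 5%, 10%, 15% and 25% (about 4, 8, 12 and 21 events in 82). If the latent score is 1 SD higher in stage 3, these fall to 13%, 27%, 38% and 54%. A score-by-arm interaction for response has power of 28%, 54% and 70% if the score acts only on NEOD001 at odds ratios of 2, 3 and 4 per SD.

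**The case against.** The strongest reply is that protocol and statistical plan are one document. Section 3.2.3 states the hypothesis, the groups, the test, the strata and the alpha, and 8.3.3 merely abbreviates it. Much of this stands. A reader might infer from 8.3.3 that no outcome contrast on biopsy scores was ever planned; the documents do not support that. But abbreviation does not explain why the one contrast kept is the uninformative one. In the same section the SF-36 paragraph does carry the confirmed-response contrast.

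A second objection also stands: the 5% rate is conditional. Section 8.3.3 names no population for this test, and the primary analysis in 8.1 is limited to patients treated for 12 months. As an illustration with about 18–20% dropout from 50 per arm, the arm test rejects in 5.1% of runs if dropout is unrelated to score, but in 9.5% or 16.5% if dropout odds in one arm rise 2- or 3-fold per SD of score. It would therefore be wrong to say the test rejects 5% of the time in any analysis set. Nor would a rejection caused by selective dropout test the 3.2.3 hypothesis.

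Third, a reader might extend the point to all biopsy work. Transcriptional profiling is separate: 3.2.3 asks there about response and progression, and 8.3.3 carries that study forward, though without a method.

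Finally, an arm comparison can show baseline balance. Description by arm serves that purpose without a test at 0.05.

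**Conclusion.** The point holds for biopsy scoring only. In 8.3.3 and the synopsis the stated test does not match the stated question. Among all randomised patients its null is true by design, and in no population does it relate entry findings to progression or to response. The core conclusion needs only the timing of biopsy and randomisation. The simulated rates illustrate it, and the power figures rest on assumed inputs and should not be read as properties of this trial.

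The fault is an inconsistency between sections, with the wrong contrast carried into the statistical section. Primary, secondary and safety conclusions are untouched. It is worth correcting before outcomes are examined, because the scores come from tissue already required for eligibility and the better analysis is nearly free.

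**What to change.** In 8.3.3 and the synopsis, replace the arm test with text along these lines:

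> The AS and the CSIS from the screening biopsy will each be related to confirmed renal response and to renal progression (Appendix 4) by the confirmatory EOS visit, in [named population], by CMH stratified by the two randomisation factors with treatment arm also accounted for. Estimates will be given with 95% CIs. A score-by-arm interaction for response will examine whether entry findings predict response to NEOD001. All of these analyses are exploratory. Scores by arm will be shown as baseline description without a hypothesis test.

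Three details need stating:

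- The time point and population for progression, since Appendix 4 sets neither.
- How each score enters the test (ordinal or named categories).
- How biopsies with fewer than the five glomeruli required for scoring are handled.

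In 3.2.3, name these contrasts in place of the loose reference to groups, and let the interaction take the place of the comparison among confirmed responders. The biopsy text in 8.3.3 should also mention the injury lesions alongside amyloid, to match 3.2.3 and Appendix 8.

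The cost is wording in three places and a little extra analysis, with no new tissue, reads or visits. The drawback is low power for progression if events are few: arm and two factors make eight strata, and with about four events most would contribute nothing. Estimates and intervals should therefore be read ahead of p-values.

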#### **8.4 Analysis of Safety Endpoints**

Study drug administration data will be listed by study site, subject number, and visit; and any dose modifications will be flagged. Means and standard deviations will be used to summarize the total number of infusions per patient, the total dose of NEOD001 received per patient, and the number of patients whose infusions were interrupted for infusion reactions.

Safety and tolerability of NEOD001 will be assessed by vital signs, duration of therapy, routine laboratory assessments, frequency and severity of AEs as assessed by CTCAE grade. We will apply descriptive statistical methods to the data, supplemented by calculation of confidence intervals if indicated. We will also display the grades and patterns of adverse events within both treatment groups.

#### **8.5. Determination of Sample Size**

This stratified randomized double-blind phase 2b study has as its primary efficacy end-point the confirmed renal response rate at 13 months after initiating therapy and is designed to detect an absolute increase in the renal response rate of 30% (from 25% in those receiving placebo to 55% in those receiving NEOD001). For the primary efficacy endpoint, the assumed true rates for NEOD001 vs placebo are 55% and 25%, respectively. Based on a chi-squared statistic to evaluate the null hypothesis at the alpha=0.05 level of significance, and assuming an 18% drop-out rate for hematologic progression requiring chemotherapy, a total sample size of 82 subjects (41 in the placebo group, 41 in the NEOD001 group) will enable us to reject the null hypothesis that the response rates for subjects receiving NEOD001 and placebo are equal with probability (power) 0.8. With 50 patients receiving placebo and 50 patients receiving NEOD001, we expect to have at least 41 evaluable patients in each group.

Of note, we are estimating the renal response rate over time in the arm not receiving NEOD001. In the relapsed setting, patients receiving lenalidomide and dexamethasone had an 18% renal response rate at 6 and 12 months; an additional 18% responded by 18 months. In relapsed patients receiving cyclophosphamide, lenalidomide and dexamethasone, 19% had renal responses, while in a phase 1/2 trial in relapsed patients (N=70) treated with bortezomib, 29% had a renal response. In the initial therapy setting, patients with renal involvement who received cyclophosphamide, bortezomib and dexamethasone (CyBorD) had a 25% renal response rate. Post-ASCT with bortezomib-based consolidation, while 50% of renal patients respond by the end of the first year, an additional 20% of renal patients respond in the second year post-ASCT. While we do not know the mix of patients who will be screened and enrolled in this trial, it is reasonable to assume that one third will be post-SCT, one third post initial and one third post second-line therapy. Allowing for a 6 month interval after chemotherapy and a 12 month interval after SCT, the weighted average of the renal response rates in these groups is 22.3%. We have chosen a higher estimate (25%) as the confirmed renal response rate in this study in patients receiving placebo.

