## 4.3 Early Treatment Discontinuation

If the subject discontinues study drug prior to the initial EOS visit, the subject should return for an ETD Visit 30 ( $\pm 5$ ) days after their final administration of study drug as per Section 6.2. If a subject fails to return for the scheduled visit, a documented effort must be made to determine the reason. If the subject cannot be reached by telephone after 2 attempts, a certified letter will be sent to the subject (or the subject's legally authorized representative, if appropriate) requesting contact with the Investigator. This letter will be submitted to the IRB for review prior to use. This information will be recorded in the study records.

If the subject discontinues study drug prior to initial EOS visit, but is willing to continue to participate in study visits, continue to collect data through the ETD Visit (i.e., 30 [ $\pm 5$ ] days after their final administration of study drug). Following the ETD Visit, subsequent clinic evaluations will be standard-of-care visits with testing as clinically warranted, usually at a minimum of every 3 months. Testing in this circumstance can be performed at a distance. Every effort should be made for the subject to return to the clinic at the month 12 time point for completion of all of the initial EOS visit assessments.

Reasons for early discontinuation from study drug treatment may include, but are not limited to:

- Hematologic progression requiring immediate initiation of chemotherapy; the chemotherapy regimen should be documented on the appropriate case report form.
- Need for organ transplant or major surgery.
- Occurrence of an AE or clinically significant laboratory abnormality that, in the opinion of the Investigator, warrants the subject's permanent discontinuation from study drug treatment; the Medical Monitor ([name]) should be notified as soon as possible of any discontinuation of study drug due to an AE.
- Suspected or confirmed pregnancy or nursing during study treatment period. Female subjects whose pregnancy test is positive at the ETD visit must be followed to term or until termination of the pregnancy.

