## 8.3 Analysis of Efficacy Endpoints

### 8.3.1 Primary Efficacy Analysis

This stratified randomized double-blind phase 2b study has as its primary efficacy endpoint confirmed renal response at the confirmatory EOS visit to evaluate 12 months of study treatment. The primary efficacy analysis will test the following hypotheses:

- $H_0$ : The confirmed renal response rate after 12 months of treatment is equal between placebo and NEOD001.
- $H_1$ : The confirmed renal response rate after 12 months of treatment is different between placebo and NEOD001.

The primary efficacy analysis of the confirmed renal response rates after 12 months of treatment with NEOD001 or placebo will be performed with the Mantel-Haenszel (MH) test at the alpha=0.05 (two-sided) level of significance. The analysis will be stratified by the randomization stratification variables. The number and percentage, with associated 95% exact confidence intervals (CI) of subjects in each category of response will be presented by treatment group. The proportional treatment difference with associated exact 95% CI will be presented.

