## **8.6 Handling of Dropouts and Missing Data**

Subjects who discontinue during the study period with ETD visits will be included in intent-to-treat but not the primary endpoint analyses. The number of such subjects will be noted in the summary table of outcomes. Analyses excluding these subjects will also be performed and described. Observed data will be included in listings and summary tables. There will be no imputation of missing data.

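### The 50-to-41 allowance covers one cause of drop-out, while the primary analysis excludes patients who stop for any cause, so power 0.8 assumes no other losses

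*Combined protocol and SAP*

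**What the plan says.** Section 8.5 sizes the trial on a comparison of two proportions: "the assumed true rates for NEOD001 vs placebo are 55% and 25%, respectively". The test is described as "Based on a chi-squared statistic to evaluate the null hypothesis at the alpha=0.05 level of significance"; section 8.3.1 supplies the sidedness, because the primary comparison "will be performed with the Mantel-Haenszel (MH) test at the alpha=0.05 (two-sided) level of significance". The target is 41 evaluable patients per arm, so that the hypothesis that the two response rates "are equal with probability (power) 0.8" is rejected. The step from randomized to evaluable patients is made by "assuming an 18% drop-out rate for hematologic progression requiring chemotherapy", and from 50 per arm "we expect to have at least 41 evaluable patients in each group". The sample-size entry in the synopsis says the same.

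The analysis rules are wider than that one cause:

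- Section 8.1 bases the primary efficacy analysis on randomized patients who receive treatment for 12 months.
- Section 8.6 says: "Subjects who discontinue during the study period with ETD visits will be included in intent-to-treat but not the primary endpoint analyses". It does not restrict this by reason, and it allows no imputation.
- Section 4.3 gives an open list of reasons for stopping study drug. Besides hematologic progression needing chemotherapy, it includes "Need for organ transplant or major surgery", adverse events or laboratory abnormalities, and pregnancy.
- Section 4.4 adds withdrawn consent, inability to comply and loss to follow-up.
- Section 4.5 allows replacement only of randomized patients who never start treatment.

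**The concern.** Section 8.5 and sections 8.1 and 8.6 do not count the same patients. The sample-size section subtracts those who leave because their hematologic disease progresses and needs chemotherapy. The analysis sections subtract those who stop before 12 months for any reason. The allowance leaves no reserve between the two, so each expected loss from another cause takes the expected evaluable number below 41.

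At stake is the accuracy of a stated design property. The protocol gives a power of 0.8 and presents 41 per arm as a minimum. Under its own exclusion rule, 41 is an average that applies only when all other losses are zero. If the trial were negative, readers would credit it with slightly more power than the plan supports.

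**Working it through.** **Inputs.** Response rates 0.55 and 0.25, alpha 0.05, power 0.8, 18% drop-out and 50 per arm (section 8.5); two-sided testing (section 8.3.1); 1:1 allocation (section 3.3).

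**Step 1: reproduce the plan's number.** The mean rate is (0.55 + 0.25)/2 = 0.40.

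- Variance term under the null: 2 x 0.40 x 0.60 = 0.48, square root 0.6928.
- Variance term under the alternative: 0.55 x 0.45 + 0.25 x 0.75 = 0.435, square root 0.6595.
- n per arm = (1.960 x 0.6928 + 0.8416 x 0.6595)² / 0.30² = 40.66, rounded up to 41.

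This matches the stated 41 per arm and 82 in total. The variants do not: a continuity correction gives 48, a one-sided test 32, and unpooled variance 38. The plan therefore used the uncorrected two-sided chi-squared test.

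**Step 2: power at 41.** Power = Φ[(0.30 x √n − 1.960 x 0.6928) / 0.6595]. At n = 41 this is Φ(0.854) = 0.803, so the stated 0.8 is reproduced.

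**Step 3: the allowance.** 50 x (1 − 0.18) = 41.0, with nothing left over.

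**Step 4: add losses from other causes.** The documents give no rate for these. The extra points below are assumptions, added to the 18% and taken as equal in both arms.

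| Assumed extra loss | Total loss | Evaluable per arm | Power |
|---|---|---|---|
| 0 points | 18% | 50 x 0.82 = 41.0 | 0.803 |
| 2 points | 20% | 50 x 0.80 = 40.0 | 0.793 |
| 5 points | 23% | 50 x 0.77 = 38.5 | 0.777 |
| 10 points | 28% | 50 x 0.72 = 36.0 | 0.749 |

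**Step 5: check the approximation.** Enumerating all outcomes of the uncorrected chi-squared test gives exact power of 0.817 at 41 per arm, 0.802 at 40, 0.772 at 38 and 0.751 at 36. On this basis the loss of one patient per arm does not matter, but from about 5 extra points onward power is below 0.80 by either method.

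**The case against.** The strongest case on the other side is that nothing has been miscalculated and that no shortfall has been shown. Much of this stands.

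- *Every stated figure reproduces.* This stands. The point concerns the definition of drop-out, not the arithmetic.
- *The shortfall is conditional.* This also stands. A reader might infer that the trial cannot reach 41 per arm. The documents do not support that: if progression requiring chemotherapy runs below 18%, the unused part absorbs other losses. Section 1.1 lets patients with hematologic progression stay on study until chemotherapy starts. Section 1.3.1 reports that no patient in the phase 1/2 study stopped for drug-related adverse events, although that says nothing about unrelated events, withdrawal, surgery or death.
- *Sections 3.3 and 3.4.1 speak of at least 100 subjects.* They also fix 50 per arm, and section 8.5 calculates from 50. This gives room to enrol more but no commitment to do so.
- *The 25% placebo rate is cautious, because section 8.5 derives 22.3%.* With 55% against 22.3%, power at 36 per arm is 0.827. That cushion depends on holding 55% fixed; if the 30-point difference is held instead (52.3% against 22.3%), power at 36 is 0.760. The plan does not offer the margin as cover for attrition.
- *Sections 4.3 and 4.4 do not define the analysis set.* Correct. Early termination in section 4.4 even covers withdrawals after the primary endpoint has been measured. The exclusion comes from sections 8.1 and 8.6; the other two only show that further causes are foreseen.
- *Section 8.3.1 requires a 95% confidence interval for the difference*, which will show the precision actually achieved. This limits the harm but does not correct the stated power.

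Two stronger readings should be set aside. A reader might treat the chance that both arms reach 41 as a measure of power. It is not one: planning on the expected number is usual, and averaging power over binomial evaluable counts at 18% loss gives 0.802. A reader might also recalculate power with discontinued patients counted as non-responders, but the plan does not specify that for its primary test.

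**Conclusion.** The point holds as a mismatch of definitions. Section 8.5 and the synopsis allow for one cause of loss; sections 8.1 and 8.6 exclude for all causes. An expected 41 evaluable per arm and power 0.8 are true together, given 18% progression, only if every other loss is zero.

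The size is modest. Compared with 0.803, power is about 1 point lower with 2 further points of loss, 2.6 lower with 5 and 5.5 lower with 10. These figures rest on progression reaching its planned 18%, equal loss in both arms, the planned rates of 55% and 25%, exactly 50 per arm, and an extra loss that is assumed rather than sourced. If the sponsor meant 18% to cover all causes, the numbers stand and only the wording is wrong.

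**What to change.** In section 8.5 and in the synopsis entry on sample size:

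1. State an all-cause non-evaluable rate that matches sections 8.1 and 8.6, or state plainly that 18% covers all causes.
2. Replace the promise of a minimum with *about 41 per arm if total loss from all causes is 18%*.
3. Report power at the resulting evaluable number, with any loss beyond 18% labelled as an assumption: 0.79 at 40 per arm (2 points), 0.78 at 38.5 (5 points), 0.75 at 36 (10 points).

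The cost is a text change in two places and a slightly less favourable stated power. No extra patients and no change of analysis are needed.
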